3.3 Study Subjects

3.3.1 Subject Disposition and Completion Status

A summary of subject eligibility and randomization (including a summary of subjects randomized but not treated with investigational product as well as treatment administered) will be provided. In addition, disposition of subjects throughout the study with respect to dose administered and completion of treatment and follow-up will be provided. This summary will include the number of subjects who discontinued treatment.

3.3.2 Demographics and Baseline Characteristics

Demographic information related to sex, age, race, ethnicity, weight, height, and BMI will be summarized by treatment group and for all subjects for the As-treated population. A summary of baseline characteristics may include, but is not limited to, duration of diabetes, diabetes complications, baseline fasting plasma glucose, and baseline HbA1c.

3.3.3 Study Drug Exposure

The duration of exposure (number of days dosed) of MEDI0382 will be summarized by treatment group with descriptive statistics and frequencies.

3.3.4 Concomitant Medications

Concomitant medications will be coded using the current World Health Organization Drug Dictionary Enhanced (WHO-DDE). The number and percentage of subjects who took concomitant medications for the highest anatomical therapeutic chemical class and preferred term will be summarized by treatment for the As-treated population. The summary of concomitant medications will include all concomitant medications taken on or after the date of first dose of investigational product or any concomitant medication started prior to first dose of investigational product that continued beyond the date of first dose of investigational product.

3.4 Efficacy Analyses

3.4.1 Primary Efficacy Endpoint(s) and Analyses

There are no primary efficacy endpoints in this study.

3.4.2 Secondary Efficacy Endpoint(s) and Analyses

3.4.2.1 Secondary Efficacy Endpoint(s)

- [REDACTED]
- [REDACTED]
- [REDACTED]
- [REDACTED]
- [REDACTED]
- [REDACTED]
- [REDACTED]

- Change in estimated HbA1c (eA1c) from baseline to the end of each week of the up-titration period and the end of the treatment extension period
- Change in plasma fasting glucose from Day -1 versus each week of the up-titration period, the end of the up-titration period, and the end of the treatment extension period
- Change in HbA1c from Day -1 to the end of the treatment extension period

- Percentage and absolute change in body weight from baseline to the end of the up-titration period and the end of the treatment extension
- Percentage and absolute change in body weight from baseline to the end of each week of the up-titration period
- Proportion of subjects achieving > 5% body weight loss from baseline to the end of the treatment extension period.

3.4.2.2 Handling of Dropouts and Missing Data

Last observation carried forward approach will be used to handle missing data for all secondary efficacy analyses. [REDACTED]

3.4.2.3 Secondary Efficacy Analyses

The secondary efficacy analyses will be based on the ITT population. The continuous secondary efficacy endpoints for the two-cohort combined analysis will be compared between the MEDI0382 and placebo arms using an analysis of covariance (ANCOVA) model adjusting for baseline value and treatment arm. For the secondary proportion-related efficacy endpoints, a logistic regression model will be used adjusting for baseline value and treatment arm. For each cohort, the secondary efficacy endpoints will be summarized without formal statistical comparisons.

[REDACTED]

[REDACTED]

[REDACTED]

[REDACTED]

[REDACTED]

[REDACTED]

[REDACTED]

[REDACTED]

[REDACTED]

[REDACTED]

[REDACTED]

[REDACTED]

[REDACTED]

[REDACTED]

[REDACTED]

[REDACTED]

[REDACTED]

[REDACTED]

[REDACTED]

[REDACTED]

[REDACTED]

[REDACTED]

[REDACTED]

[REDACTED]

[REDACTED]

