4.1.2 Inclusion Criteria

Subjects must meet all of the following criteria:

- 1 Subjects aged 18 to 74 years (inclusive) at screening
- 2 Provision of signed and dated written informed consent (with the exception of consent for genetic and non-genetic research) prior to any study specific procedures
- 3 BMI between 27 and 35 kg/m² (inclusive) at screening
- 4 HbA1c range of 6.5% to 8.5% (inclusive) at screening (Note: Subjects may be re-tested for the HbA1c entry criterion only once.)
- 5 Willing and able to self-inject investigational product for the duration of the study
- 6 Diagnosed with T2DM with glucose control managed with metformin monotherapy where no significant dose change (increase or decrease \geq 500 mg/day) has occurred in the three months prior to screening. For inclusion into Cohort 2 only, subjects prescribed oral dual therapy with a dipeptidyl peptidase-4 inhibitor, sulphonylurea, glitinide, or a sodium-glucose co-transporter 2 inhibitor in addition to metformin at screening may be eligible to enter the study following a 4-week washout period. Following wash-out, the subject must re-attend for fasting plasma glucose and HbA1c measurement to confirm eligibility prior to run-in. At this visit, an HbA1c of between 6.5% to 8.5%, inclusive **and** fasting plasma glucose level < 225 mg/dL (< 13.0 mmol/L) is acceptable. If the subject fails to meet these criteria, one repeat measurement is allowed on a different day prior to Day -10.
- 7 Female subjects must have a negative pregnancy test at screening and randomization, and must not be lactating.
- 8 Female subjects of childbearing potential who are sexually active with a male partner must be using at least one highly effective method of contraception (see [Appendix A](#) for definition of females of childbearing potential and for a description of highly effective methods of contraception) from screening and up to 4 weeks after the last dose of

investigational product. It is strongly recommended for the male partner of a female subject to also use male condom plus spermicide throughout this period. Cessation of contraception after this point should be discussed with a responsible physician. Periodic abstinence, the rhythm method, and the withdrawal method are not acceptable methods of contraception.

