4.1.7 Replacement of Subjects

Subjects will not be replaced.

For Cohort 1, up to 3 additional subjects may be screened and enter the run-in period to ensure that a sufficient number of subjects are randomized. If these subjects are not required for Cohort 1, they are available to be randomized into Cohort 2.

If the screening visit for these subjects is outside the allowed time window, they will undergo a second screening and run in period in order to be eligible for Cohort 2. When these subjects are randomized, the data from the second screening/run in (if needed) will be used for reporting.

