4.8.3.2 Secondary Efficacy Analyses

The continuous secondary efficacy endpoints for two cohorts combined analysis will be compared between the MEDI0382 and placebo arms using an analysis of covariance model adjusting for baseline value and treatment arm. For the secondary proportion-related efficacy endpoints, a logistic regression model will be used with baseline value and treatment arm.

Same endpoints for each cohort analysis will only be summarized without formal statistical comparisons.

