2.4 Sample Size

The total study sample size is 20 subjects, who will be randomized by 2 cohorts: 8 subjects in Cohort 1 and 12 subjects in Cohort 2. For each cohort, subjects will be randomized in a 3:1 ratio to the MEDI0382 arm or the placebo arm. The sample size for this study was empirically determined to obtain adequate safety and tolerability evaluation. [REDACTED]

[REDACTED]

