3 STATISTICAL METHODS

3.1 General Considerations

Data will be presented in data listings sorted by treatment, dose, subject number, and date collected, where appropriate. Tabular summaries will be presented by treatment arm. Categorical data will be summarized by the number and percentage of subjects in each category. Continuous variables will be summarized with descriptive statistics (eg, n, mean, median, SD, minimum, and maximum).

Analyses will be conducted for each cohort and for the two cohorts combined. Formal statistical modeling analysis for the secondary efficacy endpoints will be conducted for the two-cohort combined analyses. In general, unless stated otherwise, baseline will be defined as the last value prior to dosing.

Two analyses are planned for this study as follows:

- 1 A primary analysis after the up-titration period for Cohort 2, and
- 2 A final analysis after the safety follow-up period for Cohort 2.

Data analyses will be conducted using the SAS[®] System Version 9.4 or higher (SAS Institute Inc., Cary, NC) in a UNIX platform.

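### The combined-cohort ANCOVA leaves out cohort, within which subjects are randomised, and the logistic model for more than 5% weight loss (15 vs 5 subjects) has no visible provision for an empty placebo cell

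*SAP*

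**What the plan says.** **Randomisation.** SAP 2.4 and Protocol 4.8.2 plan 20 subjects, 8 in Cohort 1 and 12 in Cohort 2: "For each cohort, subjects will be randomized in a 3:1 ratio to the MEDI0382 arm or the placebo arm".

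**Where modelling is done.** SAP 3.1 states: "Formal statistical modeling analysis for the secondary efficacy endpoints will be conducted for the two-cohort combined analyses". Each cohort on its own is only summarised.

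**Continuous endpoints.** Under SAP 3.4.2.3 these are "compared between the MEDI0382 and placebo arms using an analysis of covariance (ANCOVA) model adjusting for baseline value and treatment arm". Protocol 4.8.3.2 lists the same two terms.

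**Binary endpoint.** SAP 3.4.2.1 lists "Proportion of subjects achieving > 5% body weight loss from baseline to the end of the treatment extension period". For it, SAP 3.4.2.3 says "a logistic regression model will be used adjusting for baseline value and treatment arm", and Protocol 4.8.3.2 says "a logistic regression model will be used with baseline value and treatment arm".

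**Differences between cohorts.** Protocol 4.1.2 opens one entry route to the second cohort alone: "For inclusion into Cohort 2 only, subjects prescribed oral dual therapy" may enter after a washout. Two features work against a difference. Washed-out subjects must meet HbA1c and fasting glucose limits again before run-in. Protocol 4.1.7 also says of spare Cohort 1 subjects: "If these subjects are not required for Cohort 1, they are available to be randomized into Cohort 2".

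**The concern.** There are two separate points.

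1. **Cohort.** Allocation is fixed at 3:1 inside each cohort, so a difference between cohorts cannot leak into the treatment contrast. The planned ANCOVA nevertheless leaves that difference in the residual. If cohort predicts outcome, the model's standard error is larger than the true sampling error, the interval is too wide and the test is conservative. With five placebo subjects there is little precision to spare.

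2. **Empty placebo cell.** The placebo arm has at most five subjects, because subjects are not replaced (Protocol 4.1.7). If none loses more than 5% of body weight, while some MEDI0382 subjects do, the likelihood keeps rising as the odds ratio grows. The estimate is then infinite and a Wald interval is unusable. If no rule is set in advance, the replacement method would be chosen with the data in hand, by sponsor staff who are unblinded by design (Protocol 4.6.2, SAP 2.3).

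**Working it through.** **Inputs from the documents.** Cohorts of 8 and 12, each split 3:1. This gives 6:2 and 9:3, so 15:5 combined. Arm and cohort are then exactly uncorrelated.

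**Assumed, because the visible text gives no figure.** The cohort effect, placebo responder rate, treatment effect, and alpha (two-sided 5%).

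**1. Cost of omitting cohort**

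Let d be the cohort difference in residual SDs. The cohort sum of squares is 20 × 0.4 × 0.6 × d² = 4.8d². Without cohort there are 20 − 3 = 17 residual degrees of freedom; with it, 16. The 97.5% t quantiles are 2.110 and 2.120. The ratio of CI widths, without to with cohort, is

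√((17 + 4.8d²)/17) × t(17)/t(16)

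The simulation columns come from 20,000 trials per row in the 6:2 + 9:3 layout. Power is for an assumed treatment effect of 1.5 SD.

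| d | Width ratio | Simulated ratio | Null rejection, without / with cohort | Power, without / with cohort |
|---|---|---|---|---|
| 0 | 0.995 | 0.994 | 4.9% / 4.9% | 76.1% / 75.4% |
| 0.25 | 1.004 | 1.003 | 4.8% / 5.0% | 75.1% / 75.2% |
| 0.5 | 1.030 | 1.027 | 4.3% / 4.9% | 73.8% / 75.2% |
| 1 | 1.127 | 1.120 | 3.2% / 5.1% | 67.4% / 75.6% |

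In these four settings the mean estimate was within 0.006 SD of the truth with either model, so there is no bias. The width ratio equals 1 at d = 0.184. Below that, adding cohort widens the interval, by at most 0.5%.

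How large might d be? If washout were the only source, d would equal the washed-out fraction of Cohort 2 times the washout effect. With an assumed half of Cohort 2 washed out, d = 0.25, 0.5 and 1 require washed-out subjects to differ by 0.5, 1 and 2 SD.

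**2. Chance of an empty placebo cell**

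P(0 of 5) = (1 − p)⁵.

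Adding a continuous baseline hardly changes this. The table also gives the share of 1,500 simulated trials with complete or quasi-complete separation, with the active rate assumed to be 30%.

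| Placebo rate p | P(0 of 5) | Separated: baseline + arm | Separated: cohort added |
|---|---|---|---|
| 5% | 77% | 77% | 79% |
| 10% | 59% | 60% | 62% |
| 20% | 33% | 32% | 36% |
| 30% | 17% | 18% | 22% |

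Protocol 1.4 reports a mean placebo weight loss of 1.78% in the earlier study. With normal data and an assumed SD of 1.5 to 3 points, the share above 5% is about 2% to 14%, which gives P(0 of 5) from about 92% down to 47%. That study dosed for 41 days. This one runs for up to 8 + 3 = 11 weeks, so its placebo rate may differ.

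**3. What the alternative methods would report**

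In a 2 × 2 table, Firth's penalty amounts to adding 0.5 to each cell. For 6/15 vs 0/5 the odds ratio is (6.5/9.5)/(0.5/5.5) = 7.5.

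| Responders | Firth OR (95% profile CI) | Risk difference (exact 95% CI) |
|---|---|---|
| 6/15 vs 0/5 | 7.5 (0.65 to 1,053) | 0.40 (−0.11 to 0.67) |
| 9/15 vs 0/5 | 16.1 (1.4 to 2,252) | 0.60 (0.01 to 0.85) |
| 6/15 vs 1/5 | 2.1 (0.28 to 24) | 0.20 (−0.33 to 0.56) |

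These are unadjusted. Adding a baseline unrelated to response in the first case (30 simulated baselines) gave a median odds ratio of 7.7, range 3.1 to 17.6, with an interval about as wide (0.67 to about 1,110).

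**The case against.** **The cohort term is a preference, not an error.** Omission is unbiased and conservative, no cohort effect is documented, and below 0.18 SD the added term does slight harm. Requalification after washout and the transfer of spare subjects make a 1 SD difference look remote. Cohorts are also summarised separately, so a difference would be seen. All of this is right, and it limits the point to a possible small gain. It does not remove the case for analysing by the groups used in randomisation, since the worst cost is about 0.5% in interval width.

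**A separation rule may be in unseen text.** Redactions follow both the missing-data sentence (SAP 3.4.2.2) and the model paragraph (SAP 3.4.2.3). SAP 1 defers table specifications to a programming plan that is not available. This stands: the most that can be said is that no visible text provides for an empty cell.

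**Little is lost if the odds ratio fails.** Counts and percentages by arm are planned (SAP 3.1), and continuous weight change has its own ANCOVA. This also stands, and it is why the point is minor.

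**Firth's estimate is barely informative with an empty cell.** True: the penalty largely sets it. Its merit is that it is finite and fixed in advance. The counts and risk difference carry most of the information.

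**Leaving cohort out of the logistic model looks inconsistent.** This has some force. Cohort raises the separation rate by only 2 to 4 percentage points, and Firth's penalty keeps the estimates finite anyway. Keeping the planned two terms is a judgement about how much a five-subject arm can support.

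**Conclusion.** Both points hold, and both are minor.

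Omitting cohort causes no bias at the planned allocation. Its cost depends on an unknown cohort effect: negligible to 3% in CI width up to a difference of 0.5 SD, and 13% at 1 SD.

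The empty placebo cell has more consequence. It is more likely than not at assumed placebo rates of 5% or 10%, and still about one in six at 30%. When it occurs, the planned odds ratio cannot be estimated by maximum likelihood.

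The model terms are plain in both documents. The absence of a separation rule can be judged only from unredacted text. Neither point touches the primary safety objective, the sample size was set empirically for safety and tolerability, and the visible text claims no power for these endpoints.

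**What to change.** 1. In SAP 3.4.2.3, add cohort as a fixed factor to the combined-cohort ANCOVA. Do the same for the ambulatory blood pressure ANCOVA (SAP 3.5.5.2, Protocol 4.8.4.2) wherever it is run on both cohorts together.
2. Keep baseline and arm as the terms of the logistic model for more than 5% weight loss, but fit it with Firth's penalty and report profile-likelihood intervals. Do not add cohort there.
3. In support, report counts by arm and the unadjusted risk difference with an exact unconditional 95% CI, obtained by inverting two one-sided 2.5% tests on the Farrington-Manning score statistic. Another exact method would also serve if it is named in advance.
4. If the redacted text or the programming plan already has a separation rule, the sponsor need only confirm it.

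**Cost.** SAP wording only. Cohort uses one residual degree of freedom. If it has no effect, power for the assumed 1.5 SD treatment effect falls by under 1 point (76.1% to 75.4% in the simulation). With an empty cell the Firth interval will be very wide, and the supportive risk difference adjusts for neither baseline nor cohort.

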3.5 Safety Analyses

All safety analyses will be based on the As-treated population.

3.5.1 Adverse Events and Serious Adverse Events

Adverse events (AEs) will be coded with Medical Dictionary for Regulatory Activities (MedDRA) version 21.0 or later. Analysis of AEs will include the type, incidence, severity, and relationship to investigational product summarized by MedDRA system organ class (SOC) and preferred term (PT) by treatment group as well as overall. The AEs summarized will include only treatment-emergent AEs (TEAEs), ie, those starting after the first administration of investigational product. Subjects will be counted once for specific PT or MedDRA SOC when calculating incidence rates. If the same AE PT occurs multiple times within a subject, the highest severity and level of relationship observed will be reported. If any associations of interest between AEs and baseline characteristics are observed, additional stratified results may be presented. Non-TEAEs and serious adverse events (SAEs) will be presented in the listings.

The incidence and event rate of nausea, vomiting, and nausea/vomiting on each study day during the titration period [REDACTED] will be summarized. Note that this is not just onset of a new event but includes each day the subject experiences the event excluding the AE stop day. A similar analysis including event rates will be performed for each titration dosing periods: [REDACTED]

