2 OBJECTIVES AND ENDPOINTS

2.1 Primary Objective(s) and Associated Endpoints

Table 1 Primary Objective(s) and Associated Endpoints

Type	Objective	Endpoint
Safety	Assess the safety and tolerability of MEDI0382 titrated up to the highest clinically tolerated dose (HCTD)	
 • Incidence of treatment-emergent adverse events and treatment-emergent serious adverse events through the end of the up-titration period (up to 8 weeks) and through the end of the follow-up period • Clinically important changes in 12-lead electrocardiogram, vital signs (including heart rate and blood pressure), physical examination, and clinical laboratory evaluations through the end of up-titration period (up to 8 weeks) and through the end of the follow-up period

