5 ASSESSMENT OF SAFETY

5.1 Definition of Adverse Events

An AE is the development of any untoward medical occurrence in a subject or clinical study subject administered a medicinal product and which does not necessarily have a causal relationship with this treatment. An AE can therefore be any unfavorable and unintended sign (eg, an abnormal laboratory finding), symptom (eg, nausea, chest pain), or disease temporally associated with the use of a medicinal product, whether or not considered related to the medicinal product.

The term AE is used to include both serious and non-serious AEs and can include a deterioration of a pre-existing medical occurrence. An AE may occur at any time, including run-in or washout periods, even if no study treatment has been administered.

Elective treatment or surgery or preplanned treatment or surgery (that was scheduled prior to the subject being enrolled into the study) for a documented preexisting condition that did not worsen from baseline is not considered an AE (serious or nonserious). An untoward medical event occurring during the prescheduled elective procedure or routinely scheduled treatment should be recorded as an AE or SAE.

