5.4.1 Time Period for Collection of Adverse Events

All AEs regardless of severity will be collected from randomization throughout the treatment period and including the follow-up period. All SAEs and any AEs related to study procedures will be recorded from the time of informed consent.

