5.4.4 Adverse Events Based on Examination and Tests

The results from the protocol-mandated laboratory tests and vital signs will be summarized in the CSR. An abnormal laboratory finding (including ECG finding) that requires medical intervention by the investigator, or a finding judged by the investigator as medically significant should be reported as an AE. If clinical sequelae are associated with a laboratory abnormality, the diagnosis or medical condition should be reported (eg, renal failure, hematuria) not the laboratory abnormality (eg, elevated creatinine, urine red blood cell increased)

If deterioration in a laboratory value/vital sign is associated with clinical signs and symptoms, the sign or symptom will be reported as an AE and the associated laboratory result/vital sign will be considered as additional information. Wherever possible the reporting investigator uses the clinical, rather than the laboratory term (eg, anemia versus low hemoglobin value). In the absence of clinical signs or symptoms, clinically relevant deteriorations in non-mandated parameters should be reported as AE(s).

Any new or aggravated clinically relevant abnormal medical finding at a physical examination as compared with the baseline assessment will be reported as an AE

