- Laboratory tests. A specific laboratory investigation (if performed) has confirmed the relationship?

In difficult cases, other factors could be considered such as:

- Is this a recognized feature of overdose of the investigational product?
- Is there a known mechanism?

Causality of ‘related’ is made if following a review of the relevant data, there is evidence for a ‘reasonable possibility’ of a causal relationship for the individual case. The expression ‘reasonable possibility’ of a causal relationship is meant to convey, in general, that there are facts (evidence) or arguments to suggest a causal relationship.

The causality assessment is performed based on the available data including enough information to make an informed judgment. With limited or insufficient information in the case, it is likely that the event(s) will be assessed as ‘not related’.

Causal relationship in cases where the disease under study has deteriorated due to lack of effect should be classified as no reasonable possibility.

Relationship to Protocol Procedures

The investigator is also required to provide an assessment of relationship of SAEs to protocol procedures on the SAE Report Form. This includes nontreatment-emergent SAEs (ie, SAEs that occur prior to the administration of investigational product) as well as treatment-emergent SAEs. A protocol-related SAE may occur as a result of a procedure or intervention required during the study (eg, blood collection, washout of an existing medication). The following guidelines should be used by investigators to assess the relationship of SAEs to the protocol:

Protocol related: The event occurred due to a procedure/intervention that was described in the protocol for which there is no alternative etiology present in the subject’s medical record.

Not protocol related: The event is related to an aetiology other than the procedure/intervention that was described in the protocol (the alternative aetiology must be documented in the study subject’s medical record).

Appendix C National Institute of Allergy and Infectious Disease and Food Allergy and Anaphylaxis Network Guidance for Anaphylaxis Diagnosis

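### SAP 3.5.1 defines treatment-emergent AEs by start date alone, so an AE recorded before first dose that worsens or becomes serious on treatment is left out of the TEAE/TESAE summaries behind the primary endpoint

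*SAP*

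**What the plan says.** Protocol 2.1 gives the first primary endpoint as "Incidence of treatment-emergent adverse events and treatment-emergent serious adverse events through the end of the up-titration period", and likewise through follow-up. Protocol 4.8.4.1 summarises treatment-emergent AEs without defining the term, and protocol 4.8.1 leaves further analysis detail to the SAP. The working definition is therefore the one in SAP 3.5.1: "The AEs summarized will include only treatment-emergent AEs (TEAEs), ie, those starting after the first administration of investigational product". It has no clause for worsening. The same section sends non-TEAEs to the listings.

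The protocol sets two starting points for AE recording in section 5.4.1. The general one is: "All AEs regardless of severity will be collected from randomization throughout the treatment period and including the follow-up period". The earlier one is: "All SAEs and any AEs related to study procedures will be recorded from the time of informed consent". Appendix B, in its examples of procedures and interventions to which an SAE may be related, names washout ("eg, blood collection, washout of an existing medication"). The only subjects with a planned washout are those entering Cohort 2 on dual oral therapy.

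On worsening, protocol 5.1 says: "The term AE is used to include both serious and non-serious AEs and can include a deterioration of a pre-existing medical occurrence". Section 5.4.4 requires an AE report for "Any new or aggravated clinically relevant abnormal medical finding at a physical examination", judged against baseline. Section 5.4 says that an AE which evolves into a serious one goes on the SAE form, but it assigns no new onset date.

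**The concern.** The protocol opens AE records before dosing, and the SAP then classifies each record by its start date. An AE already on record at first dose keeps its pre-dose date. If it goes from mild to severe on treatment, or becomes serious, the rule as written makes it a non-TEAE. It then misses the incidence, severity and relationship tables for AEs.

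The primary purpose of the trial is to describe safety and tolerability, and worsening on treatment is part of what those tables are meant to show. The alternative is to leave the matter to each site's habit of opening or not opening a new record, and then the classification of a primary-endpoint event rests on an unwritten convention. Sponsor staff on the study are unblinded (protocol 4.6.2, SAP 2.3), so a convention settled late could be settled with treatment known. That is a reason to write the rule down in advance. Nothing in the documents suggests that it would be misused.

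**Working it through.** The plan gives no figure to reproduce. The check is a reading of the rules against each other, followed by simple arithmetic.

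**1. Which AE records can exist before first dose**
- SAEs and procedure-related AEs: from consent. Table 5 starts screening at Day -25, so the window is about 25 days in the ordinary case. For Cohort 2 washout subjects, the Table 5 footnote extends screening to Day -42. The synopsis instead allows up to 42 days ahead of a 10-day run-in, which gives 42 + 10 = 52 days. The window is therefore about 6 to 7 weeks.
- All other AEs: from randomization only. Protocol 4.6.1 requires dosing within 24 hours of assignment, so this window is at most a day.

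**2. How the SAP rule treats each case**

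| Situation | Result under SAP 3.5.1 |
|---|---|
| Medical-history condition, not yet an AE, deteriorates after first dose | New AE under protocol 5.1 or 5.4.4; if dated at the worsening, it is a TEAE |
| Pre-dose AE resolves, then recurs after first dose | If recorded as a new occurrence, it starts after first dose and is a TEAE |
| Pre-dose AE continues and increases in severity | Start date is before dosing; listed only, unless the site opens a new record |
| Pre-dose non-serious AE becomes serious after first dose | Protocol 5.4 moves it to the SAE form with no new onset date; not a TESAE by the SAP rule |

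The last two rows are the gap. Both documents deal with the same AE occurring several times in a subject, but neither says how to date a rise in severity within one continuing AE.

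**3. Planned arm sizes (SAP 2.4, 3:1 in each cohort)**
- MEDI0382: 8 × 3/4 + 12 × 3/4 = 6 + 9 = 15.
- Placebo: 8 × 1/4 + 12 × 1/4 = 2 + 3 = 5.

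**4. Weight of one missed subject**
- Incidence of a given preferred term: 1/15 = 6.7 percentage points on MEDI0382; 1/5 = 20 points on placebo.
- Overall TEAE incidence: the same shift, but only if the subject has no other TEAE. Protocol 1.4 reports that 82% and 83% of subjects in two earlier cohorts had at least one treatment-related AE. If those rates carried over, and were independent of the missed event, about 100 − 82 = 18% or 100 − 83 = 17% would have no such event. On MEDI0382 a missed subject would therefore usually be counted already.

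**5. How often it might happen**

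The documents give no rate for AEs that start before dosing and worsen afterwards. As an assumption only, let a proportion p of the 20 subjects have one. The expected number is 20p, and the chance of at least one is 1 − (1 − p)^20.

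| Assumed p | Expected number | Chance of at least one |
|---|---|---|
| 2% | 0.4 | 33% |
| 5% | 1 | 64% |
| 10% | 2 | 88% |

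Even at the top of this range the count is about two subjects.

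**The case against.** The strongest reply is that the protocol already brings most worsening into the count. A deterioration is an AE in its own right under section 5.1 (it "can include a deterioration of a pre-existing medical occurrence"), and an aggravated examination finding must be reported under 5.4.4. Dated at the worsening, both pass the SAP rule. This stands. A reader might infer from SAP 3.5.1 that every pre-existing condition that worsens on drug drops out of the primary endpoint, but the documents do not support that. The reply does not reach an event already open as an AE before first dose.

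Second, the pre-dose window for ordinary AEs is at most 24 hours. This also stands and removes some tempting examples. Mild nausea on Day -1 before randomization is not collected unless it is serious or procedure-related, so later nausea can be a new AE. The longer window remains for SAEs and procedure-related AEs.

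Third, worsening is visible elsewhere. SAP 3.5.4 and 3.5.5 analyse laboratory values, vital signs, ambulatory blood pressure and ECG against baseline whatever the AE dates, and such changes are the second primary endpoint. Non-TEAEs are listed and, with 20 subjects, can be read one by one. The dose-escalation criteria in protocol 3.1.3.2 refer to AEs and SAEs, not to TEAEs. No test of TEAE incidence is planned. A reader might infer that worsening of a pre-dose AE can appear in no table at all, which would go too far. The day-by-day nausea and vomiting summary counts days with the event and not only onsets, and neither it nor the table of discontinuations due to AEs says how pre-dose onsets are treated. Protocol 4.8.4.1 also promises an SAE summary without a treatment-emergent limit. None of this restores the event to the TEAE incidence, severity and relationship tables.

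Fourth, the eCRF instructions or the statistical programming plan may contain a dating rule. They were not available for this review, so it cannot be said that no such rule exists in the study. The SAP's own wording is nonetheless complete as it stands, and no document seen here qualifies it.

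**Conclusion.** The point holds in a narrow form and is worth correcting. AEs recorded before first dose that increase in severity or become serious on treatment are left out of the TEAE and TESAE summaries, and appear only in listings, unless sites happen to open a new record. This covers SAEs and procedure-related AEs from consent, including those from washout in Cohort 2, and any AE between randomization and first dose.

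The likely size is small. Few such events are expected, and no rate can be derived from the documents. The arms are small enough for one case to show in a preferred-term table. The shifts of 6.7 and 20 points should not be read as the expected effect on overall TEAE incidence, because they apply there only when the missed event is the subject's sole TEAE.

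The conclusion assumes the planned arms of 15 and 5, that a continuing AE keeps one record with its first onset date, and that no dating convention elsewhere overrides SAP 3.5.1.

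**What to change.** In SAP 3.5.1, define a TEAE as an AE that starts after the first dose, or that was present before the first dose and increases in severity or becomes serious after it. Use the same definition for TESAEs.

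Add an eCRF completion instruction that worsening is recorded under its own date, most simply as a new AE record opened on that date, so that the rule can be programmed. If a new record is always opened, the current start-date wording would already capture the event. The definition is still worth stating, so that the endpoint does not depend on site practice. Counting each subject once per preferred term, as SAP 3.5.1 already does, prevents double counting in the incidence tables.

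State also whether the nausea and vomiting day counts and the table of AE discontinuations include events that began before dosing.

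The cost is a short SAP edit and one recording instruction. The downside is a slightly higher TEAE count and a few extra AE records. Dosing, visits and sample size are unchanged.
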